The aim, as described in the protocol, is to provide transparent and comparable medical evidence that can support health care policy makers to take informed decisions on the provision of health services for the treatment of hearing loss. A brief summary of the protocol follows.

3. Objectives of the Study

The primary objective is to evaluate the change in health-related quality of life following CI treatment by using the generic Health Utilities Index Mark III (HUI 3) multi-attribute index score. All pairwise comparisons are of interest i.e. preimplant to 12 months postimplant, preimplant to 18 months postimplant, and the change from 12 to 18 months.

A secondary objective involves evaluating the impact of CI treatment in the elderly on domains that may be associated with healthy aging and overall well-being such as

- hearing ability (using the Capabilities of Auditory Performance (CAP-II) test, the Speech Spatial and Qualities (SSQ) questionnaire, the Hearing Handicap Inventory for the Elderly Scale (HHIE-S), speech recognition tests in the quiet and in noise, pure tone audiometry (PTA) and sound field thresholds (SFT))
- independence (using the Lawton-instrumental Activities of Daily Living (L-iADL) tool)
- cognition (using the Mini Mental State Examination (MMSE) score, the Digit Symbol Substitution (DSST) test and the Trail Making Test version B (Trail B))
- falls (using the Timed Up and Go test (TUG))
- depression (using the Geriatric Depression Scale-15 (GDS-15), and the De Jong Loneliness Scale)
- CI usage measures.

All pairwise comparisons between time points, as defined above, are of interest here also.

A tertiary objective is to identify healthcare resource utilisation that is impacted by comparing costs post CI treatment with those prior to treatment.

For all of these objectives, interest is also in whether various demographic variables are associated with the change in outcome scores observed.

In summary:

Primary hypothesis

CI treatment significantly improves the overall health related quality of life of elderly individuals compared to their pre-implant condition (and again from 12 to 18 months following surgery) as measured by the HUI3 multi-attribute score.

Secondary hypothesis

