7.3 Statistical Analyses

Primary hypothesis analysis

If comparison between the HUI3 multi-attribute score from pre-surgery to only one follow-up time point is of interest then paired t-tests can be used. A check of the assumption that the change from pre-surgery is normally distributed should be performed. The distribution of change scores should be approximately symmetric. The disadvantage of this approach is that it uses only complete data at any given pair of time points

If all pairwise differences are of interest (as per the hypothesis) and the scatter plot of change over time appears (close to) linear then a linear mixed-effects model with a fixed effect of time (treated as a continuous variable) and a random effect for participant should be used to explain the change in response variable over time. Tukey pairwise differences between time points can be specified (we recommend using the *multcomp* package in R as it does not require balanced designs i.e. the same sample size across time points). Appropriate diagnostic checks of the linear mixed-effects model (for example, normality of the residuals, normality of the random effects) should always be undertaken. An advantage of the linear mixed-effects model is that it uses all available data even for subjects who have dropped out at a given time point and then returned.

If the change over time was evidently not linear from the scatterplot of response against time then alternative approaches should be used. For example:

1. A quadratic or cubic term for time could be added to the linear mixed-effects model and checked to determine if that improves the fit of the model (eg via reduced AIC, better diagnostic checks).
2. The pre-surgery HUI3 multi attribute score value can be used as a predictor variable (with the response variable then only including the post-surgery visits). A significant coefficient would imply that the amount of change is dependent on the pre-surgery score. An interaction between baseline score and post-surgery time points could also be included – this would show whether the change in mean score over time is impacted by baseline score. This approach will remove any participant without baseline data from the analysis.

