3. Use visit as categorical variable. This essentially fits a linear model between time points but makes no assumption that the change from baseline is linear. Tukey pairwise comparisons between all pairs of time points (if time is found to be a significant predictor) are straight forward with this approach and should be undertaken using the *multcomp* package in R, which does not require balanced designs.

Secondary hypotheses analysis

The approach described for the primary hypothesis can be used for all continuous responses described in the secondary hypotheses. Failure of the assumptions may indicate that that a linear model is not appropriate and that other response distributions need to be explored. At this stage it is likely best that a statistician is consulted.

For ordinal responses such as the CAP II score an ordinal mixed-effects model including time as a fixed effect and participant as a random effect. The results of this model will show the

odds of being in a higher category compared to the current category over time (this interpretation is package dependent).

Tertiary hypotheses analysis

The approach described for the primary hypothesis is appropriate here also for continuous outcomes. As described above, for ordinal responses an ordinal mixed-effects model including time as a fixed effect and participant as a random effect. If the response variable is nominal (categorical without natural ordering) a multinomial mixed-effects model can be used and for binary responses a mixed effects logistic regression can be undertaken.

If only one pair of time points is of interest then for binary responses a test for the change in proportions can be undertaken and for continuous responses a paired t-test can be undertaken.

Analysis for other hypotheses

The other hypotheses involve the effect of covariates on a response and on the change over time. To assess the effect of a given covariate (for example age, gender, etc) the covariate can be added to the model as a fixed main effect in addition to the time variable and as an interaction with the time variable.

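### SAP 7.3, alternative 2: a baseline coefficient different from 0 does not show that change depends on baseline; with the post-surgery score as response the null value is 1

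*SAP*

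**What the plan says.** SAP section 7.3 (Statistical Analyses) first proposes a mixed model that is linear in time for the HUI3 multi-attribute score. It then adds: "If the change over time was evidently not linear from the scatterplot of response against time then alternative approaches should be used". Three examples follow. In the second, the pre-surgery score becomes a predictor, "with the response variable then only including the post-surgery visits". The interpretation rule comes next: "A significant coefficient would imply that the amount of change is dependent on the pre-surgery score". No null value is named, so significance has its usual meaning of a coefficient different from 0. The SAP goes on: "An interaction between baseline score and post-surgery time points could also be included".

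The primary-hypothesis approach is carried over to other outcomes. For secondary outcomes: "The approach described for the primary hypothesis can be used for all continuous responses described in the secondary hypotheses". For tertiary outcomes: "The approach described for the primary hypothesis is appropriate here also for continuous outcomes".

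**The concern.** The rule suits a model whose response is the change score. Alternative 2 uses the post-surgery score itself. In that model a coefficient above 0 is what one expects whenever the same person's scores are correlated over time, whether or not gain varies with the starting level.

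An analyst who follows the sentence could therefore report that benefit depends on pre-surgery health status when it does not. That is a statement about which patients gain more, in a study meant to inform policy makers, referring professionals and candidates. Because the approach is reused for continuous secondary and tertiary outcomes, the same misreading could recur there.

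**Working it through.** **Inputs**
- Effect 0.10, SD of change 0.25, 90% power, 5% level: SAP section 5. The two-sided test is in Protocol section 9.
- Second SD of change, from the sponsor's earlier data set in Protocol section 9 (n = 67, mean change 0.165, 95% CI 0.109 to 0.221): half-width (0.221 − 0.109)/2 = 0.056, and 0.056/1.997 × √67 = 0.230.
- N = 90: 100 enrolled less 10%, the upper end of the attrition range in Protocol section 8.6.7.
- Baseline SD of HUI3: not in the documents. Assumed 0.15 to 0.25.

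**The plan's own figures.** The disputed sentence gives no number. The sample sizes reproduce: with d = 0.10/0.25 = 0.4, an exact paired t-test needs N = 68 at 5% (power 0.902) and N = 88 at 0.05/3 = 0.0167 (power 0.903).

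**Algebra (no assumed figures).** Let E[post | pre] = a + b × pre. Subtracting pre gives E[change | pre] = a + (b − 1) × pre. Change is unrelated to baseline if and only if b = 1. In one simulated data set (88 participants, true b = 1), the mixed model gave a baseline coefficient of 0.983 (SE 0.101, p < 10⁻²⁰) with the score as response, and −0.017 (SE 0.101, p = 0.87) with change as response. The two coefficients differ by exactly 1. The first would be read as dependence under the SAP sentence; the second shows none.

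**Simulation.** 20,000 trials per row, N = 90, two-sided 5%, residual variance = SDchange² − (1 − b)² × SDpre².

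| True b | SD of change | Baseline SD | Rejects b = 0 (SAP reading) | Rejects b = 1 |
|---|---|---|---|---|
| 1 (same expected gain for all) | 0.23 | 0.15 | 99.99% | 4.9% |
| 1 | 0.23 | 0.20 | 100% | 5.1% |
| 1 | 0.23 | 0.25 | 100% | 5.2% |
| 1 | 0.25 | 0.15 | 99.98% | 5.1% |
| 1 | 0.25 | 0.20 | 100% | 5.1% |
| 1 | 0.25 | 0.25 | 100% | 4.9% |
| 0 (change falls one-for-one with baseline) | 0.23 | 0.15 | 4.8% | 100% |
| 0 | 0.23 | 0.20 | 4.9% | 100% |
| 0 | 0.25 | 0.15 | 4.9% | 100% |
| 0 | 0.25 | 0.20 | 5.0% | 100% |
| 0 | 0.30 | 0.25 | 5.2% | 100% |
| 0 | 0.35 | 0.25 | 5.3% | 100% |

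With b = 0 and a baseline SD of 0.25, the residual variance is positive only if the SD of change exceeds 0.25, hence the larger values in the last two rows. At b = 1 the SAP reading declares dependence in 99.6% to 100% of trials from N = 68 to N = 100. Averaging the two post-surgery visits (assumed residual correlation 0.5 or 0.8) leaves the pattern unchanged.

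**Why the rule almost always fires at b = 1.** The coefficient is significant once the pre/post correlation exceeds t/√(N − 2 + t²), which is 0.239, 0.210, 0.207 and 0.197 at N = 68, 88, 90 and 100. At b = 1 the implied correlation is SDpre/√(SDpre² + SDchange²). This runs from 0.15/√(0.15² + 0.25²) = 0.51 to 0.25/√(0.25² + 0.23²) = 0.74, far above the threshold.

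**Does other text correct the sentence?** The interaction does not. With slopes b₁₂ and b₁₈ at the two post-surgery visits, it tests b₁₈ − b₁₂ = 0, which concerns only change from 12 to 18 months. The covariate method under the other hypotheses, where a covariate enters "as a fixed main effect in addition to the time variable and as an interaction with the time variable", is a different model.

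**The case against.** The algebra is not in dispute. The case on the other side concerns reach and presentation.

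- **An optional fallback.** Alternative 2 is one of three examples, used only if the time course is clearly not linear. No endpoint, hypothesis or sample size rests on dependence on the baseline score. The stated covariate interest is demographic ("interest is also in whether various demographic variables are associated with the change in outcome scores observed") and has its own method. This stands, and it limits the weight of the point.
- **The headline rate belongs to one value, b = 1.** The documents do not show where b lies. At b = 1 the post-surgery SD must exceed the baseline SD by a factor √(1 + SDchange²/SDpre²), that is by 36% to 94% for the SDs used, on a scale capped at 1.00. If the two SDs are equal, b equals the pre/post correlation, is below 1, and observed change does depend on baseline. At b = 0.5 (N = 88, SD of change 0.25, baseline SD 0.15, two visits averaged) both tests reject in 91% of trials, and both are right. This stands too. But a rule that gives the same verdict at b = 0.5 and b = 1 cannot tell the two apart.
- **The SAP does not state the converse.** It never says that a non-significant coefficient means no dependence. True; the b = 0 rows show only that the rule fails to detect dependence there.
- **The corrected test is not clean either.** The 5% rate assumes an error-free baseline. If true change is unrelated to true baseline and baseline reliability is 0.7 to 0.9 (assumed), the expected coefficient is 0.7 to 0.9, and the test of b = 1 rejects in 9% to 89% of trials (21% to 55% at reliability 0.8). This stands, and the replacement wording has to say so.

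None of this makes the sentence correct.

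**Conclusion.** The concern holds. The interpretation rule is wrong for the model it accompanies, and that conclusion rests on algebra alone. Where expected gain does not depend on the starting level, following the rule gives a false statement of dependence in practically every trial of this size. The percentages, unlike the algebra, rest on the assumed baseline SD, an error-free baseline and normally distributed scores.

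The damage is confined to a side conclusion about baseline score, and arises only if alternative 2 is used, for HUI3 or for a continuous secondary or tertiary outcome. The primary pre/post comparisons, the sample size and the demographic covariate analyses are untouched. It should be corrected, but it does not threaten the main result.

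**What to change.** Replace the sentence in alternative 2 with wording such as:

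> A coefficient different from 0 shows only that pre- and post-surgery scores are associated. Dependence of observed change on the pre-surgery score is tested as coefficient = 1 (equivalently, slope = 0 with change from baseline as the response) and reported with its 95% CI. Regression to the mean alone pushes the coefficient below 1, so a value below 1 is not by itself evidence that lower-scoring patients gain more.

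If the baseline-by-visit interaction is kept, test the slope against 1 at each visit, and note that the interaction itself concerns only the 12-to-18-month change.

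The cost is one SAP sentence, plus a short note if the interaction is used. Data, models and software stay the same.

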7.3 Multiple Comparisons

The statistical methods described above involve many comparisons using related measures on the same sets of participants. This can result in occasional spuriously significant results. Analyses specifically for the purpose of publication should

1. limit the number of analyses undertaken and presented or
2. use a more stringent level of significance that is defined a priori. For example, a significance level of 0.01 could be used rather than the usual 0.05 significance level. A very limited number of pre-specified analyses would generally not require multiple comparison corrections.
3. a Bonferroni-type correction could be applied in which the significance level is adjusted for the number of comparisons.

References

Prince, Martin J et al. (2015). The burden of disease in older people and implications for health policy and practice. **The Lancet**, 385(9967): 549 – 562.
